9.1 Assignment of Preferred Terms and Original Terminology

For classification purposes, preferred terms will be assigned by the Sponsor to the original terms entered on the eCRF using the most up-to-date version of the MedDRA terminology for adverse events and diseases and the International Non-Proprietary Name Drug Terms and Procedures Dictionary for treatments and surgical and medical procedures.

10. STUDY COMMITTEES

A Data Safety Monitoring Board (DSMB) has been utilized to ensure patient safety and will consist of external clinicians who are experts in the disease area and 1 external statistician. The DSMB reviewed available safety data approximately every 3 months. The DSMB had the option to change the data review schedule as deemed needed. Details of the DSMB's responsibilities and logistics were outlined in the charter. Safety monitoring by an independent DSMB has ceased following the results of the primary efficacy analysis of the Phase III study, GO28141.

12. ETHICAL ASPECTS

12.1 Local Regulations/Declaration of Helsinki

The investigator will ensure that this study is conducted in full conformance with the principles of the “Declaration of Helsinki” or with the laws and regulations of the country in which the research is conducted, whichever affords the greater protection to the individual. The study must fully adhere to the principles outlined in “Guideline for Good Clinical Practice” ICH Tripartite Guideline [January 1997] or with local law if it affords greater protection to the subject. For studies conducted in the USA or under US IND, the investigator will additionally ensure adherence to the basic principles of “Good Clinical Practice” as outlined in the current version of 21 CFR, subchapter D, part 312, “Responsibilities of Sponsors and Investigators”, part 50, “Protection of Human Subjects”, and part 56, “Institutional Review Boards”.

In other countries where “Guideline for Good Clinical Practice” exists, Roche and the investigators will strictly ensure adherence to the stated provisions.

Patients who comply with the requirements of the protocol, are tolerating study treatment, and have not developed disease progression may be offered dosing beyond Cycle 1 at the investigator’s discretion after a careful assessment and thorough discussion of the potential risks and benefits of continued treatment with the patient. Such patients may have the option to continue RO8155426 in combination with cobimetinib for up to 1 year as long as the above-mentioned conditions are met. If the study is terminated (see Section 4.7), however, study drugs may not be offered after study termination.

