- To characterize Day 1 and steady-state pharmacokinetics of cobimetinib when administered in combination with vemurafenib and to characterize the steady-state pharmacokinetics of vemurafenib administered alone and in combination with cobimetinib

Secondary Objectives

- To assess the anti-tumor activity of the vemurafenib and cobimetinib combination
- To assess the mechanisms of response and resistance to vemurafenib and cobimetinib combination therapy (including genetic alterations of RAS, RAF, and MEK)
- To assess the BRAF^{V600E} mutation status of patients who progressed on vemurafenib monotherapy
- To identify factors that may pre-dispose patients to squamous cell carcinoma (SCC) development

- To assess the pharmacodynamic (PD) effects of vemurafenib and cobimetinib when administered in combination, as measured by changes in fluorodeoxyglucose–positron emission tomography (FDG-PET)
- To assess the PD effects of vemurafenib and cobimetinib when administered in combination, as measured by changes in molecular biomarkers in sequential paired biopsies
- To assess the PD utility of FDG-PET and changes in molecular biomarkers in sequential paired biopsies in a subset of patients (up to n=20) treated with single-agent cobimetinib

STUDY DESIGN

This is an open-label, multicenter, Phase Ib, dose-escalation study designed to assess the safety, tolerability, and pharmacokinetics of continuous daily oral dosing of vemurafenib administered in combination with orally dosed cobimetinib administered daily for 14 consecutive days followed by 14 days off (14/14), for 21 consecutive days followed by 7 days off (21/7), or as a continuous daily dose. Patients with previously untreated, BRAF^{V600E} mutation-positive, locally advanced/unresectable or metastatic melanoma OR those who have progressed on vemurafenib monotherapy immediately prior to enrolling in this trial are eligible. Patients in the former category who were previously treated must have had no prior exposure to any BRAF or MEK inhibitor therapy. Treatment will continue until disease progression, unacceptable toxicity, or any other discontinuation criterion is met (Section 4.5). Vemurafenib will be dosed daily, and cobimetinib will be dosed on a 14/14, 21/7, or a continuous schedule in a 28-day cycle. Alternate dosing regimens and schedules may be interrogated depending on the nature and timing of the toxicities encountered.

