Treatment will continue until disease progression, unacceptable toxicity, or any other discontinuation criterion is met (Section 4.5). There may be circumstances in which one of the study drugs is discontinued (e.g., as outlined in dose modification, Section 6.1). In the case of permanent cobimetinib discontinuation, patients previously treated with vemurafenib should come off the study. In the case of permanent vemurafenib discontinuation, it will be possible for the patient to continue treatment with single-agent cobimetinib until disease progression, unacceptable toxicity, or any other discontinuation criterion is met (see Section 4.5). In patients without prior treatment for locally advanced and unresectable or metastatic melanoma, permanent discontinuation of either drug while continuing the other will not be grounds for study discontinuation.

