There will be no opportunity to evaluate the pharmacokinetics of cobimetinib monotherapy in this study except in those patients who are treated in the cobimetinib monotherapy arm. Cobimetinib will be combined with vemurafenib on Day 1, and for all patients, PK assessments will occur on Day 1 for cobimetinib (0, 0.5, 1, 2, 4, and 6 hours post-dose) and Day 14 (0, 0.5, 1, 2, 4, 6, and 8 hours post-dose) for both agents to characterize exposure for each drug after single dose and at steady state, respectively. A PK assessment will be made on Day 8 to characterize the approach to steady state. Additional PK samples will be collected during the 14-days off period for cobimetinib to evaluate the elimination properties ($t_{1/2}$ clearance) of the drug in the presence of vemurafenib for those patients treated on a 14/14 schedule only.

Lastly, for both compounds, periodic steady-state PK samples will be collected in subsequent cycles to ensure patients are exposed to constant drug levels throughout the study. For additional information on PK sampling, refer to [Table 10](#) and [Table 11](#).

3.6 Rationale for Dosing beyond Cycle 1

The ethical conduct of studying cancer therapeutics requires that patients have the opportunity to continue study treatment for as long as the treatment is effective and tolerable. Therefore, patients enrolled in this study who comply with the requirements of the protocol and are tolerating study treatment may continue dosing until disease progression, unacceptable toxicity, or any other discontinuation criterion is met (Section 3.1.6).

3.7 Rationale for Collection of Patient Specimens for Molecular Analyses (Biopsies, Plasma, Blood)

Roche is committed to the collection of patient specimens in all clinical study protocols. The objective of molecular analyses (biomarker profiling) is to enable development of treatments specifically targeted for optimal patient benefit (personalized healthcare). The rationale of planned molecular analyses is explained below. However, since knowledge of the drug, the disease, new markers, and technologies are evolving, the definitive list of analyses may be modified based on new information as the information becomes available.

Investigation of Response/Resistance Markers

To identify causes for resistance, molecular analyses will be performed to investigate BRAF, CRAF, PTEN, RAS, and MEK, as well as further key pathway markers at the protein, mRNA, and genetic level.

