4.5 Criteria for Premature Withdrawal and Discontinuation

Patients have the right to withdraw from the study at any time for any reason.

In cases where the patient decides to prematurely discontinue study treatment (“refuses treatment”), he/she should be asked if he/she can still be contacted for further information. The outcome of that discussion should be documented in both the medical records and in the eCRF. If lost to follow-up, the investigator should contact the patient or a responsible relative by telephone followed by registered mail to establish as completely as possible the reason for the withdrawal. A complete final evaluation at the time of the patient’s withdrawal should be made with an explanation of why the patient is withdrawing from the study.

When applicable, patients should be informed of circumstances under which their participation may be terminated by the investigator without the patient’s consent. The investigator may withdraw patients from the study in the event of intercurrent illness, adverse events, treatment failure after a prescribed procedure, lack of compliance with the study and/or study procedures (e.g., dosing instructions, study visits), cure or any reason where it is felt by the investigator that it is in the best interest of the patient to be terminated from the study. Any administrative or other reasons for withdrawal must be documented and explained to the patient. Any patient who discontinues will be encouraged to return to the study center for a study completion visit.

Additionally, patients must discontinue study treatment if they experience any of the following:

- Disease progression per investigator assessment using RECIST v1.1
- Intolerance of vemurafenib and cobimetinib combination therapy or cobimetinib monotherapy after discussion with the Medical Monitor
- Pregnancy

Patients should return to the clinic for a study completion visit 28 days after study treatment discontinuation (see Section 5 for assessments that are to be performed at that visit). The primary reason for discontinuation must be recorded on the appropriate eCRF.

Study Discontinuation

Roche has the right to terminate this study at any time. Reasons for terminating the study may include, but are not limited to, the following:

- All enrolled patients have discontinued study treatment.
- The incidence or intensity (severity) of adverse events in this or other studies indicates a potential health hazard to patients.

Post-Trial Access

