14. Patients will receive cobimetinib on a 14-days on/14-days off schedule, on a 21-days on/7 days off schedule, or on a continuous schedule (qd) in a 28-day cycle. For study evaluations performed earlier than the scheduled day, patients cannot restart cobimetinib until they have had the minimum number of days without cobimetinib dosing. For patients on the 14/14 and 21/7 dosing schedules of cobimetinib, the minimum numbers of days without cobimetinib are 14 and 7, respectively. For both investigational drugs, dosing will continue until disease progression, consent withdrawal, or unacceptable toxicity. Dispense a sufficient number of vemurafenib and cobimetinib capsules/tablets to last until the next visit and provide a medication diary. Extra capsules/tablets may be dispensed if there is a reasonable possibility that the patient's next visit may be delayed (e.g., because of inclement weather or distance of patient's home from study center). Instruct patient to record the time and date they take each study drug dose in the diary and to return all unused capsules/tablets at each study visit to assess compliance. Collect and review medication diary, collect unused capsules/tablets, and assess compliance at each subsequent visit.
15. Review and capture of all concomitant medications will be performed at each study visit. Concomitant medications are defined as any prescription medications or over-the-counter preparations used by a patient within 7 days before screening and continuing through the study completion visit.
16. After signing the informed consent, adverse events will be collected as detailed in Section 7.1.2. All adverse events will be recorded until 28 days after the last dose of study treatment or until initiation of another anti-cancer therapy, whichever occurs first.
17. During long-term follow-up, survival assessments should be performed every 12 weeks until *death* after last study treatment.

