5.8 Dosing beyond Progression

Dosing beyond progression is not recommended. Only under special circumstances when it is felt that the patient may clinically benefit by continued therapy should dosing beyond progression be considered. If it is judged by the investigator, in consultation with the Sponsor, that it is in the best interest of the patient, the patient may continue dosing of both vemurafenib and cobimetinib at the current dose or on cobimetinib alone. All patients who continue cobimetinib monotherapy dosing beyond progression will be dosed at 60 mg daily on a 21/7 schedule and will continue to be followed in their previously assigned cohort. Patients, who prior to progression could only tolerate a dose of cobimetinib below 60 mg daily, may continue dosing at their previously tolerated dose and schedule.

Special circumstances can be defined by, for example, cystic lesions, mixed responses, and new brain metastases that are treatable during the study with stereotactic radiotherapy or surgery but that do not require whole brain radiotherapy. If brain metastases are to be treated with stereotactic radiotherapy/gamma knife, vemurafenib and cobimetinib should be held 1 day prior to the procedure and may resume 1 day after the procedure is completed.

Patients who receive study therapy beyond progression must continue to undergo study visits, laboratory assessments and safety assessments and tumor assessments as specified in Sections 5.3 and 5.4. Tumor assessment scans collected post-progression will not be sent to ICON and the tumor assessment forms in the eCRF does not need to be completed.

Patients who receive study therapy beyond progression may stop study therapy anytime the investigator judges that the patient is no longer benefiting from the study therapy. Patients are required to stop study therapy if continued disease progression is documented in subsequent tumor assessments.

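### Section 12.1 offers the combination for at most one year, while the synopsis, Sections 3.1, 3.1.6 and 3.6 and Table 9 set no time limit

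*Combined protocol and SAP*

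**What the plan says.** Section 12.1 is in Part II, on ethics and administration. It describes patients who comply with the protocol, tolerate treatment and have not progressed. They may be offered dosing after Cycle 1 at the investigator's discretion, and may have the option to continue vemurafenib "in combination with cobimetinib for up to 1 year as long as the above-mentioned conditions are met".

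The other statements on treatment duration carry no time limit:

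- Synopsis (Study Design) and Section 3.1: "Treatment will continue until disease progression, unacceptable toxicity, or any other discontinuation criterion is met (Section 4.5").
- Section 3.1.6, on dosing beyond Cycle 1: "Treatment will continue until disease progression, unacceptable toxicity, or any other discontinuation criterion is met".
- Section 3.6, the rationale for dosing beyond Cycle 1: compliant, tolerating patients "may continue dosing until disease progression, unacceptable toxicity, or any other discontinuation criterion is met". The reason given is ethical, namely that "patients have the opportunity to continue study treatment for as long as the treatment is effective and tolerable".
- Table 9, footnote 14: "For both investigational drugs, dosing will continue until disease progression, consent withdrawal, or unacceptable toxicity".

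Section 4.5 holds the stop criteria. It says that "patients must discontinue study treatment if they experience any of the following" and then lists progression by RECIST, intolerance of study treatment after discussion with the Medical Monitor, and pregnancy.

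**The concern.** Consider a patient who is compliant, tolerating both drugs and free of progression when a year has passed. Section 3.1.6 says that treatment goes on. Section 12.1 can be read as saying that the option has run out. A site cannot follow both.

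What is at stake is mainly patient care and the coherence of the protocol. Someone with metastatic melanoma who is still benefiting could be taken off the combination because of one sentence in an administrative section, although Section 3.6 presents open-ended dosing as an ethical requirement. Section 4.5 adds that the sponsor does not intend to supply either drug after the study or after an earlier withdrawal. Commercial availability in several countries (Sections 1.2.1 and 1.3.1) softens that point.

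**Working it through.** The plan has no figure to reproduce here. The check is a comparison of texts, with one unit conversion.

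**Step 1: is the limit current text?** Yes. It stands in the body of Version L, not in the summary of changes.

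**Step 2: set the duration statements side by side.**

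| Place | What ends dosing | Time limit |
|---|---|---|
| Synopsis, Study Design | progression, toxicity, other criterion in 4.5 | none |
| 3.1 | same | none |
| 3.1.6 | same | none |
| 3.6 | same, by reference to 3.1.6 | none |
| Table 9, footnote 14 | progression, consent withdrawal, toxicity | none |
| 12.1 | loss of compliance, tolerance or freedom from progression | 1 year, combination only |

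**Step 3: follow the cross-references for a hidden limit.** Section 3.6 points to 3.1.6, and 3.1.6 points to 4.5. Besides the three mandatory stops, 4.5 covers the patient's own decision, withdrawal by the investigator (intercurrent illness, adverse events, treatment failure, non-compliance, cure, or the patient's best interest) and termination of the study by the sponsor. None is triggered by elapsed time. Section 3.11, on the end of the study, has no time criterion either. The references to another discontinuation criterion therefore do not bring in the one-year limit.

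**Step 4: locate the limit in cycles.** Cycles last 28 days (Section 3.1.1).

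- Counted from Cycle 1, Day 1: 365 / 28 = 13.04, about 13 cycles.
- Counted from the end of Cycle 1: 28 + 365 = 393 days, and 393 / 28 = 14.04, about 14 cycles.

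Section 12.1 does not say which start applies. These figures show only where the limit would fall. They do not measure impact, because the documents give no time-on-combination figure from which to compute the share of patients who would reach it.

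**Step 5: check what the limit could touch.** The DLT window closes at Day 28 (Section 3.1.3), at least 365 − 28 = 337 days before the limit. The escalation rules and MTD determination (3.1.4, 8.2.6), the sample size (8.3) and Tables 13 and 14 do not depend on treatment beyond that window in a way that a one-year limit would alter.

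**The case against.** The strongest reply is that 12.1 is permissive. Patients may be offered continued dosing and may have an option. Nothing there says that they must stop, and no procedure is given for stopping at one year. The sentence sits in Part II, while the Part I sections that govern dosing agree with one another. A site working from Part I would not stop a patient at one year, so this looks like leftover wording rather than two competing treatment rules. Two clerical slips in the same paragraph support that view: a drug code that differs from the one on the synopsis page, and a reference to Section 4.7, the replacement policy, for study termination. The trial is also descriptive, with no hypothesis test and no power calculation (8.2.1, 8.2.2, 8.3).

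Much of this stands. It limits the claim to what 12.1 could be read as requiring, and it keeps the severity low. It does not remove the conflict: a permission with an upper bound is still bounded, and stale wording in the current protocol is still text that a site may follow.

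A reader might also see a second contradiction, because 12.1 requires freedom from progression while Section 5.8 says that in special circumstances "the patient may continue dosing of both vemurafenib and cobimetinib at the current dose or on cobimetinib alone". The documents do not support treating this as a fault of 12.1. The synopsis, 3.1, 3.1.6, 3.6, footnote 14 and 4.5 all leave out the same narrow exception, and 5.8 itself advises against dosing beyond progression in general.

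**Conclusion.** Wrong as written, low impact. One sentence in 12.1 sets an upper limit on the combination that five duration statements lack and that no criterion in 4.5 supports. This conclusion rests on the current text alone and needs no numerical assumption.

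Three stronger readings are tempting and should not be drawn:

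- *Patients were stopped at one year.* Nothing in the documents shows that the limit was applied.
- *Follow-up for PFS or duration of response was cut short.* Footnote 10 of Table 9 words tumor assessments as taking place on treatment, but Section 5.3.2 leaves the frequency of post-baseline assessments to local standard of care without that restriction. An effect is possible but not established.
- *All study treatment ends at one year.* The limit names the combination only. Single-agent cobimetinib, which 3.1.6 and 5.8 allow in some circumstances, is not covered by it.

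**What to change.** In Section 12.1, delete the one-year limit and state that continuation follows Sections 3.1.6 and 4.5. A cross-reference to 5.8 is optional. While that paragraph is open, two clerical corrections can be made: the vemurafenib code should be RO5185426 rather than RO8155426, and the reference for study termination should be to Sections 4.5 and 14 rather than 4.7. The consent form, which was not available for this review, should be checked for the same limit.

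The cost is one paragraph of wording and the consent-form check.

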12.2 Informed Consent

Written Informed Consent from Subjects:

12.2.1 Main Study Informed Consent

It is the responsibility of the investigator, or a person designated by the investigator [if acceptable by local regulations], to obtain signed informed consent from each subject prior to participating in this study after adequate explanation of the aims, methods, anticipated benefits, and potential hazards of the study.

The investigator or designee must also explain that the subjects are completely free to refuse to enter the study or to withdraw from it at any time, for any reason.

The Case Report Forms (CRFs) for this study contain a section for documenting subject informed consent, and this must be completed appropriately. If new safety information results in significant changes in the risk/benefit assessment, the consent form should be reviewed and updated if necessary. All subjects (including those already being treated) should be informed of the new information, given a copy of the revised form and give their consent to continue in the study.

For the subject not qualified or incapable of giving legal consent, written consent must be obtained from the legally acceptable representative. In the case where both the subject and his/her legally acceptable representative are unable to read, an impartial witness should be present during the entire informed consent discussion. After the subject and representative have orally consented to participation in the trial, the witness' signature on the form will attest that the information in the consent form was accurately explained and understood.

For US-IND studies: In a life-threatening situation where a subject is unconscious or otherwise unable to communicate, the emergency is such that there is not enough time to obtain consent from the subject's legally acceptable representative, and there is no other or better treatment available, it is permissible to treat the subject under protocol with consent of both the investigator and another physician not involved in the study, with appropriate documentation submitted to the IRB within 5 days. If this collaboration is not immediately possible, there must be a written evaluation by a physician independent of the study and the appropriate documentation be submitted to the IRB within 5 days of treating the subject. In addition, the subject or his/her legally acceptable representative should be informed about the trial as soon as possible and consent to continue, giving written consent as described above.

For non-US-IND studies: In a life-threatening situation where a subject is unconscious or otherwise unable to communicate, the emergency is such that there is not enough time to obtain consent from the subject's legally acceptable representative, and there is no other or better treatment available, it is permissible to treat the subject under protocol with consent of the investigator, with appropriate documentation that the IEC had approved the procedures used to enroll subjects in such situations. In addition, the subject or his/her legally acceptable representative should be informed about the trial as soon as possible and consent to continue, giving written consent as described above.

